## Protocol Summary

**Study Device:** Clear & Brilliant Touch

**Protocol Number:** XXXXXXXX

**Projected Study period:** Initiation Date: November 2022 Completion Date: November 2023

**Study Duration:** 12 months

**Purpose:** To evaluate the efficacy and safety of the combination 1927nm Low-Powered Diode laser and topical cysteamine cream for treatment of melasma on the face.

### Procedure:

#### Visit 1 (Screening and Initial Treatment Visit)

- Verify that subject is qualified to participate in the study.
- Ask subject to give personal information, such as name, date of birth, race and ethnicity.
- Review medical and dermatology (skin) history, including history of previous treatments to area being treated.
- Review past and current medications and skin care products.
- See how tall subject is and how much subject weighs
- If subject is a woman and can have children, urine will be tested to see if subject is pregnant. The study doctor or study staff will tell subject if pregnancy test results are positive. The results of the pregnancy testing must be negative in order for subject to be in the study.
- Supply patient with topical cysteamine cream and review instructions for its use
- Identify and examine the area (i.e, side) of face to which the Diode 1927 nm laser will be used (mapping)
- Take photos of face
- Perform grading of melasma
- Perform treatment according to guidelines stated in protocol
- Schedule the next study visit

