**Objectives:**

- A. To evaluate the efficacy of the Clear & Brilliant Permea laser system in combination with topical cysteamine
  - a. To assess for improvement of melasma after completion of three treatments as determined by the treating clinician and objective measures
  - b. To evaluate subject's satisfaction with melasma treatment and assessment of improvement after three treatments
  - c. To evaluate the length of treatment.
- B. To evaluate the safety of melasma treatment in all skin types using the Clear & Brilliant Permea laser in combination with topical cysteamine
  - a. To evaluate the immediate response to treatment
  - b. To evaluate the subject's assessment of comfort associated with treatments
  - c. To determine the rate of adverse events for the treatment group as a whole

**Study Design:** Single Center, Prospective, With Before-After Analysis

**Study population:** Twenty healthy male or female patients, 18-74 years of age, of all skin types with melasma on the face that wish to be treated. Each subject will receive topical cysteamine cream which they will be instructed to use once a day at home. In addition, one side of the face will be randomly selected for treatment with laser. Patients will receive three monthly treatments, at 4-6 week intervals, on the selected side of the face with the Clear & Brilliant Permea laser. The treatment duration including pre and post treatment procedures is estimated to be 90 minutes per subject. Subjects will return for a follow-up visit 3 months after the initial treatment for a total of four visits. The treatment plan will be the same regardless of the subject's skin type. Four passes, at high setting will be performed.

During the first and fourth visit, the areas of treatment will be photographed with a digital camera under controlled conditions. Subject improvement will be assessed via investigator and subject grading at visit 1 and 4. Improvement in melasma will be assessed by blinded evaluators who will review pre and post treatment photographs taken with VISIA® Skin Analysis System for facial imaging (Canfield Scientific Inc) from visit 1 and 4. Side effects (including pain, redness, dryness, and hyperpigmentation) will be assessed and recorded at visits 2, 3, 4.

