**Clinical Evaluations:**

The following clinical evaluations will be performed throughout the study as detailed in the visit procedure summary. In the event a treatment is to be administered at a visit the scoring should be done before any laser therapy or drug application. The same investigator should complete the evaluations for a given subject throughout the study. If this becomes impossible a sub investigator with overlapping experience with the subject and the study should complete the evaluations.

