**Criteria of Evaluation (Study Endpoints):**

In person assessment by treating physician and photographic assessment in which blinded dermatologists compared photographs of the individual's face areas at baseline and visit 4 from all patients in the study.

Clinical Endpoints:

- In person assessment by treating physicians will measure change in mMASI of the subjects face at between baseline (visit 1) and week 4.
- The Global Aesthetic Improvement Scale (GAIS), a 5-point scale rating global aesthetic improvement in appearance, compared to pretreatment, as judged by the investigator and the subject will also be assessed. The rating categories used on this scale will be “worse” “no change” “improved” “much improved” and “very much improved”. The percent ranking improvements in the Investigator and Subject GAIS scale from baseline (visit 1) to visit 4 will be compared.
- Photographic assessment by two blinded dermatologists will measure changes will assess improvement in melasma by mMASI score. In addition, an investigator quartile improvement score from baseline to week 12 (0 – 0%, no improvement; 76%-100% - very significant improvement) will be assessed.

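### Nothing in the protocol keeps the lasered side unknown until the in-person baseline mMASI is scored, and the Visit 1 list places identification of that side first

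*Protocol*

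**What the plan says.** **Allocation.** The study population text under Objectives says that "one side of the face will be randomly selected for treatment with laser". It does not say when the side is selected or when the site learns it.

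**Visit 1 order.** The list has twelve unnumbered bullets. The eighth is "Identify and examine the area (i.e, side) of face to which the Diode 1927 nm laser will be used (mapping", the ninth is photography, the tenth is "Perform grading of melasma", and the eleventh is treatment.

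**Timing of scoring.** Clinical Evaluations gives the only rule: "In the event a treatment is to be administered at a visit the scoring should be done before any laser therapy or drug application". That section adds that "The same investigator should complete the evaluations for a given subject throughout the study".

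**Who scores mMASI.** The study endpoints name two assessments. The first is in person: "In person assessment by treating physicians will measure change in mMASI of the subjects face at between baseline (visit 1) and week 4". No masking is stated for these physicians. The second uses photographs: "Photographic assessment by two blinded dermatologists will measure changes will assess improvement in melasma by mMASI score". The study population text confirms that blinded evaluators review the Visit 1 and Visit 4 images.

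The in-person endpoint names week 4, whereas the visit lists schedule grading at Visits 1 and 4 (week 12). That mismatch is a separate matter. The same baseline score is used either way.

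**The concern.** The primary objective compares laser plus cysteamine with cysteamine alone within the same face, and the first hypothesis expects the larger mMASI improvement on the lasered side. Area and darkness are ordinal judgements made by eye. The in-person endpoint is a change, so the baseline grade enters it directly. If the rater knows which side will be lasered and grades it slightly harsher, the excess is later counted as improvement on that side with no laser effect behind it.

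Once a grade has been recorded with the side known, no analysis of change can separate the shift from real severity. Masking the in-person follow-up score is hard when only one side receives laser. Masking the baseline score needs only the right order of steps.

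**Working it through.** **1. Does any text close the gap?** Take a site that maps the side, then grades, then treats. It meets the rule that "the scoring should be done before any laser therapy or drug application", it follows the Visit 1 list, and it respects random selection of the side. It is fully compliant, and its baseline is graded with the allocation known. No other section orders baseline scoring against disclosure of the side.

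**2. Which scores are exposed?**

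| Assessment | Rater | Baseline exposed? | Follow-up exposed? |
|---|---|---|---|
| In-person mMASI | Treating physician, no masking stated | Yes, if the side is known at grading | Yes, whatever the Visit 1 order |
| Photographic mMASI | Two blinded dermatologists | No | No |

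**3. How a baseline shift enters the endpoint.** Let both sides have true baseline B, let the follow-up scores be F(laser) and F(control), and let the laser side's baseline be over-graded by e. The recorded between-side difference in change is

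[(B + e) − F(laser)] − [B − F(control)] = [F(control) − F(laser)] + e.

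The shift passes through in full.

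**4. Scale of one grade step.** The mMASI table scores each malar region as 0.3 × A × D. Assume A = 4 and true D = 2 on both sides, with both falling to D = 1:

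- True baseline: 0.3 × 4 × 2 = 2.4
- Baseline over-graded by one darkness step: 0.3 × 4 × 3 = 3.6
- Follow-up: 0.3 × 4 × 1 = 1.2
- Recorded change: 3.6 − 1.2 = 2.4 on the laser side, 2.4 − 1.2 = 1.2 on the other

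The spurious difference is 1.2 points. One darkness step is worth 0.3 × A, which runs from 0.3 points (A = 1) to 1.8 points (A = 6).

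**5. Effect on the test.** The plan's own figure, 20 subjects for 80% power, cannot be reproduced because no effect size or SD is given. Solving backwards with the noncentral t at two-sided 5% gives an implied paired effect of 0.66 SD. The normal approximation is (1.960 + 0.842)/√20 = 0.63.

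Suppose, purely as an assumption, that baseline over-grading averages b SDs of the paired difference and there is no true effect. The rejection rate is P(|T| > 2.093), with T noncentral t on 19 df and noncentrality b√20:

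| b (assumed) | b√20 | Two-sided rejection rate, n = 20 |
|---|---|---|
| 0 | 0 | 5.0% |
| 0.1 | 0.447 | 7.1% |
| 0.2 | 0.894 | 13.6% |
| 0.3 | 1.342 | 24.7% |

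The documents give no SD, so the points in step 4 cannot be converted into b. The table shows sensitivity only. It is not an estimate.

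**The case against.** **The list may not be a sequence.** This carries weight. The bullets are unnumbered, and the list for Visits 2 and 3 puts photographs after treatment and scheduling, while the Photographs section puts them before treatment. The section on mapping and pretreatment evaluation describes only photographs, so mapping may not be a distinct earlier step. A reader might infer that the protocol commits every site to grading with the side known; the documents do not support that. What stands is that no rule prevents it, and the only listed order points that way.

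**Blinded readers also score mMASI.** Correct, and this limits the point. A reader might infer that all baseline data are compromised, photographs included, since these too follow mapping in the list. The documents do not support that either: the imaging system standardises position, lighting and camera settings, and the readers are blinded. However, the in-person mMASI is listed as an endpoint in its own right, and the photographic score is not given precedence over it.

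**Examining the side before grading might suggest that the side is chosen on appearance.** A reader might infer this, but the protocol says the side is random, and examining an already assigned side is consistent with that.

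**The illustration is a strong case.** It is: a full darkness step over a whole malar region, at baseline only. It shows direction and mechanism, not a likely size.

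**Follow-up remains unmasked, so reordering changes little.** In-person follow-up scoring does stay open to bias, possibly the larger one. That is no reason to leave the baseline open when it can be closed.

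**Conclusion.** The point holds for one measure: the in-person baseline mMASI graded by the treating physician. The protocol allows that score to be set with the lasered side known, and over-grading of that side would be recorded as extra improvement there. The blinded photographic mMASI is untouched.

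The size is unknown. One malar darkness step is worth 0.3 to 1.8 points depending on area, and the error rates above rest on assumed shifts. The conclusion assumes that the in-person score is compared between sides, as the first hypothesis requires, although the mMASI table gives a whole-face total. Confidence is moderate, because the Visit 1 order is implied rather than fixed. With the baseline masked, its contribution to the bias is zero. The in-person change score would still not be free of bias, because its follow-up half is unmasked.

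**What to change.** In the Visit 1 list, move melasma grading ahead of the mapping step. In Clinical Evaluations, add a sentence such as: the in-person baseline mMASI is recorded so that left and right can be compared, and is completed and locked before the side assigned to laser is disclosed. The photographs need not move for this purpose.

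The cost is a small change in visit flow, with no added visit or procedure. It also needs a recording convention for the forehead and chin, which the mMASI table does not split by side; the malar regions are already separate.

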#### Visit 2 and 3 (Week 4 and 8)

- Assess side-effects of the treatment at initial visit
- See how tall subject is and how much subject weighs
- Perform treatment according to guidelines stated in protocol
- Schedule the next study visit
- Take photos of face

#### Visit 4 (Week 12)

- Assess side-effects of treatment
- See how tall subject is and how much subject weighs
- Take photos of face
- Perform grading of melasma
- Post-treatment questionnaire
- Evaluation of photos comparing visit 1 and 4 to be performed

**Risks and Discomforts:** Blistering, edema, erythema and local pain are typical reactions to laser treatment. A lesser possibility exists for hyperpigmentation, hypopigmentation scarring, and/or infection. These conditions may or may not resolve over time. As with any method of tissue destruction, there is a risk of infection and of scarring, which is minimized with proper wound care. Eye injury due to the use of the laser is a risk to the subject as well as the operator. The subjects may experience partial or permanent hair reduction. Risks of the topical include temporary irritation, burning or heating up sensation that resolves within 30 minutes

**Benefits:** The subjects may or may not show improvement of melasma on the treatment sites. There is no guarantee of success.

#### **Background:**

Melasma is a commonly acquired hyperpigmentary condition characterized by brown spots on sun exposed areas of the face. Treatment of melasma can be challenging as many patients are refractory to therapy, while others experience a chronic or relapsing course. Melasma also significantly impact patients' quality of life with many reporting feelings of frustration, embarrassment, and depression related to their condition. Mainstay of treatment includes topical skin-lightening and brightening agents such as hydroquinone, tranexamic acid, retinoids, azelaic, kojic and ascorbic acids, as well as various chemical peels, laser and light-based therapies. Current gold standard is a triple combination cream consisting of topical hydroquinone, tretinoin, and fluocinolone, along with broad-spectrum sunscreen. However, use of topical hydroquinone is associated with adverse events including irritation and a paradoxical exogenous ochronosis with prolonged use, making its use challenging. Hence, for this difficult, and often recalcitrant disease, additional therapeutic options are needed.

Topical cysteamine is safe, generally well tolerated, and can be used continuously without treatment holidays. Multiple studies have demonstrated its efficacy in the treatment of melasma, including two double-blind, randomized, and placebo controlled clinical trials. Combination therapy of lasers with lightening agents have been shown to augment melasma treatment. However, data on combination laser and topical cysteamine is sparse, and no controlled or split-faced studies have been published. Thus, we aim to investigate combined topical cysteamine with laser, compared with topical cysteamine alone to assess whether this adjuvant therapy can improve the efficacy of cysteamine in the treatment of melasma.

The primary objective of our study is to determine the efficacy of combined topical cysteamine cream with a 1927 diode non-ablative laser (Clear + Brilliant Permea®; Solta Medical, Inc.), compared to topical cysteamine alone in the treatment of melasma. This efficacy will be assessed using modified Melasma Area and Severity Index (mMASI) scores, a validated physician assessment tool, at baseline and at follow up visits at week 4, 8 and 12 as well as Investigator Global Assessments. Secondary objectives also include an assessment of patient satisfaction which will be evaluated via patient questionnaires distributed to patients at baseline and at week 12. In addition, impact on quality of life will also be assessed utilizing the melasma quality of life scale (MELASQoL) questionnaire which will be administered to patients at baseline and at week 12.

Multiple studies have demonstrated the efficacy of topical cysteamine in the treatment of melasma. Mansouri et al. conducted a double-blind, randomized, controlled clinical study, which included 50 melasma patients, and demonstrated significant efficacy of topical cysteamine in the treatment of melasma. One comparative trial demonstrated that topical 5% cysteamine, though safe and well-tolerated, was less effective than topical 4% hydroquinone in the treatment of facial melasma; however, a later published response indicated that the concentration of cysteamine may have been less than the reported 5%. A single-blind, randomized comparative trial of 54 melasma patients found no statistically significant difference in the efficacy of topical cysteamine compared to topical tranexamic acid; however, cysteamine was better tolerated amongst the patients. Finally, Karrabi et al. also found that cysteamine 5% cream showed greater efficacy than the gold standard, modified Kligman's formula, in their randomized, double-blind trial of 50 patients with epidermal melasma.

Non-ablative fractional lasers (NAFL) target water-containing tissues to create microthermal zones (MTZ) in the dermis and induce neocollagenesis and remodeling without damage to the epidermis. These lasers have been shown to be effective in the treatment of melasma with a more durable response compared to other lasers and energy-based devices. The efficacy of combined topical agents with NAFL in the treatment of melasma has also been thoroughly studied. Mohamed et al. investigated the use of fractional Er:YAG laser with topical steroids compared to the laser alone in 22 patients with melasma and found significantly improved outcomes with the use of combined therapy. Tournalaki et al. reported the combination of fractional 1540nm Erbium-glass laser with a triple-combination cream (hydroquinone 4%, retinoic acid 0.03%, hydrocortisone butyrate 0.1%) resulted in marked improvement in 67.1% and moderate improvement in 21.1% of patients who were previously resistant to triple-combination cream alone. Several authors have also shown that laser-assisted delivery with lowenergy, low-density 1927 nm fractional thulium fiber laser combined with topical tranexamic acid results in significant improvement in melasma. Combination of the same laser with 4% hydroquinone cream demonstrated more than 50% improvement in 60% of melasma patients after one treatment in another retrospective study. In addition, a retrospective review of 11 patients with melasma and subtle or sub-clinical telangiectatic erythema found improvement in 6 out of 11 patients treated with the 595-nm pulsed dye laser (PDL) combined with the 1927-nm fractional low-powered diode laser. Per authors, patients in this study were continued on various topical therapies including hydroquinone 4% cream or gel although compliance was not measured.

Thus far, one case series has been published investigating the combination of topical cysteamine with laser. Johnson et al treated three melasma patients with nightly cysteamine and monthly treatments with a 650-microsecond nd-YAG 1,064-nm laser, resulting in all patients reporting satisfaction and persistent results noted two months later. In summary, while the efficacy of topical cysteamine has been demonstrated and combination laser treatment with multiple topical agents such as tranexamic acid and hydroquinone have been thoroughly studied, there have been no controlled studies investigating combination therapy with topical cysteamine.

We hypothesize that addition of 1927-nm fractional low-powered diode laser therapy to topical 5% cysteamine will result in significantly greater improvement in both the clinical appearance of melasma as well as patient satisfaction, compared to topical cysteamine alone. Specifically, we hypothesize:

- 1) Patients will experience improvement in their melasma on both treated sides, with greater improvement noted with combined topical and 1927-nm fractional low-powered diode laser treatment noted on their mMASI scores at weeks 4, 8 and 12.
- 2) Patients will report improvement in satisfaction on patient questionnaires on both treated sides, however there will be greater change in satisfaction noted with combined topical and 1927-nm fractional low-powered diode laser treatment at week 12 compared to baseline (week 0)

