#### Sample Size Calculation:

A sample size is calculated to test the null hypothesis with a one-sided paired t-test for simplicity, although the final analysis may employ a statistically more powerful model.

We calculate that for a two-sided alpha level of 5%, a sample size of 20 subjects will enable us to test the null hypothesis with 80% power. In order to enable the analysis and take into account the potential for dropout we may include up to 25 patients.

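### The protocol fixes no single deciding measure and time for its primary objective, and its sections disagree on which mMASI time and which global rating count

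*Protocol*

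**What the plan says.** - **Background, primary objective (Protocol).** Efficacy of the combination against cysteamine alone is judged on mMASI "at baseline and at follow up visits at week 4, 8 and 12 as well as Investigator Global Assessments".
- **Background, hypothesis 1.** Greater improvement on the laser side is expected, "noted on their mMASI scores at weeks 4, 8 and 12".
- **Criteria of Evaluation (Study Endpoints).** "In person assessment by treating physicians will measure change in mMASI of the subjects face at between baseline (visit 1) and week 4". The list continues with "The Global Aesthetic Improvement Scale (GAIS), a 5-point scale rating global aesthetic improvement in appearance", of which "The percent ranking improvements in the Investigator and Subject GAIS scale from baseline (visit 1) to visit 4 will be compared". It adds mMASI from photographs read by two blinded dermatologists, and "an investigator quartile improvement score from baseline to week 12". No item is called primary.
- **Objectives, study population paragraph.** "Subject improvement will be assessed via investigator and subject grading at visit 1 and 4". The visit lists agree: grading of melasma stands under Visit 1 and Visit 4 (week 12), and not under Visits 2 and 3 (weeks 4 and 8).
- **Sample Size Calculation.** The trial is sized with a single paired t-test, "for a two-sided alpha level of 5%, a sample size of 20 subjects" giving 80% power.

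**The concern.** A 5% level protects a claim only when it is clear in advance which result decides it. Here the sample size presumes one test, while the primary objective lists at least four results and gives no rule for combining them. One of the four carries a name that no endpoint uses, and two further investigator ratings (the GAIS and the quartile score) could each be taken to be it. Two of the three mMASI times have no scheduled grading. A reader of the final report could not tell whether the result put forward as primary was the one intended from the start. That matters in a trial of 20 to 25 subjects whose stated use is to guide practice.

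**Working it through.** **1. The sections side by side**

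| Section | mMASI time | Global rating | Marked primary |
|---|---|---|---|
| Background, primary objective | weeks 4, 8, 12 | Investigator Global Assessments | four results, none ranked |
| Background, hypothesis 1 | weeks 4, 8, 12 | none | none |
| Study Endpoints | in person: week 4; photographs: time not stated in that sentence | investigator and subject GAIS to visit 4; quartile score to week 12 | none |
| Objectives and visit lists | grading at visits 1 and 4 (week 12) | grading at visits 1 and 4 | not applicable |

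Week 12 is the only post-baseline visit with scheduled grading. Week 4 in the endpoint list may be a slip for visit 4, but the text does not settle that. Photographs are listed at visits 2 and 3, but the blinded review compares visits 1 and 4 only.

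**2. The plan's own figure**

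The protocol gives no effect size and no standard deviation of the paired difference, so the 20 subjects cannot be reproduced. Solving backwards for 80% power with n = 20 gives these standardised paired effects:
- Two-sided 5%: 0.66 by the noncentral t; the normal approximation is (1.960 + 0.842)/√20 = 0.63.
- One-sided 5%: 0.58 by the noncentral t; the normal approximation is (1.645 + 0.842)/√20 = 0.56.

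Both are shown because the section names a one-sided test and a two-sided level. Either way the calculation is for one test.

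**3. If any one of the results may count**

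With k independent tests the false-positive rate is 1 − 0.95^k:
- k = 2: 9.75%
- k = 3: 14.3%
- k = 4: 18.5%

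The scores come from the same patients, so they are correlated. The protocol gives no correlation, so the values below are assumed. Simulated paired t-tests (n = 20, equal correlation, two-sided 5%, 200,000 runs) gave:

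| Assumed correlation | Four results | Three mMASI times only |
|---|---|---|
| 0.5 | 15.7% | 12.7% |
| 0.7 | 13.4% | 11.1% |
| 0.9 | 9.5% | 8.5% |
| 0.95 | 8.0% | 7.5% |

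Counting only false claims in favour of the laser, the four-result rate runs from 9.6% (independent) to 4.0% (correlation 0.95), against a nominal 2.5%.

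**4. If only scheduled measures are counted**

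That leaves two tests: week-12 mMASI and one global score. Simulated normal statistics gave 9.7% at correlation 0, 9.1% at 0.5 and 8.4% at 0.7.

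**5. If all four must be positive**

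The error cannot exceed 5%, since each result must pass its own 5% test. With no true difference on any of the four, it was 2.5% or less for correlations up to 0.95. Power is then the weak point. If each test has 80% power (an assumption), joint power lies between 0.8^4 = 41% (independent) and 80% (perfectly correlated).

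**6. If the level were split over four**

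0.05/4 = 0.0125 per test. At the implied effect of 0.66 and n = 20, power for each test falls from 80% to about 58%.

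**The case against.** Three objections carry weight.

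- **No section says that any one result suffices.** The wording joins the measures with 'as well as' and 'and', and hypothesis 1 can be read as requiring all three times. This stands. A reader might infer that the false-positive risk is simply well above 5%, but the documents do not support that as a fact. It follows only from an any-one rule that is nowhere written.
- **Multiplicity rules often sit in a statistical analysis plan.** The protocol also allows a more powerful final model, which could give one overall test across visits. This stands as far as it goes, and the absence of a multiplicity method is not the complaint here. Naming the primary measure and time, however, belongs in the protocol, and the sections that do name times contradict each other. An analysis plan can choose between them but cannot make them agree.
- **An investigator-rated global scale is defined.** The GAIS has five named categories and runs from visit 1 to visit 4. This stands too. A reader might infer that the global measure is missing altogether. The better reading is an unreconciled name: the GAIS may be what is meant, but the quartile score fits as well and the text does not choose.

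Independence is also implausible for repeated scores on the same faces, so 18.5% is a ceiling and not an estimate.

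**Conclusion.** The point holds as a defect of specification. No single measure and time decides the primary objective, and the Background, Objectives, visit lists and Study Endpoints sections disagree on it. The stated 5%, 80% and 20 subjects fit together only if one test decides, and none is named.

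The size depends on a rule that the protocol does not give:
- **Any one of four results counts:** about 8% to 16% false positives for assumed correlations of 0.95 to 0.5, and 18.5% at most.
- **Week-12 mMASI or one global score counts:** about 8% to 10%, for assumed correlations of 0.7 to 0.
- **All must succeed:** no inflation, but power could fall below 80%.

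The correlations are assumptions throughout, and so is equal 80% power per test in the last case. The contradictions between sections rest on no assumption.

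**What to change.** 1. In the primary objective (Background), name one test: the between-side difference in mMASI change from baseline to week 12, at two-sided 5%. Take Investigator Global Assessments out of that sentence.
2. State which mMASI source decides, the in-person physician score or the blinded photographic score. Both are in the endpoint list, and leaving both would keep two tests.
3. State how mMASI is scored per side. The scoring table separates left and right for the malar areas only and defines just a whole-face total.
4. Make the investigator GAIS, the quartile score and any week 4 and 8 mMASI secondary. Report them with confidence intervals, and not as alternative evidence of primary success. Use one name for the global rating throughout.
5. Bring hypothesis 1 and the week 4 time in the endpoint list into line with this.

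The cost is protocol wording, with no added visits or subjects. The downside is that the global rating and the earlier visits lose primary status.
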